7.2. Clinical Laboratory Tests

7.2.1. Definitions

Laboratory parameters of hematology, serum chemistry and urinalysis will be investigated: all analyses will be done on SI-converted values as available in the database.

Imputations of numerical values expressed as characters

In case a laboratory test result is censored (no numeric value is available, but only a verbatim term), the following rules are applied:

- ‘<x’ or ‘>x’: a numeric value will be imputed by the cut-off value decreased or increased with one unit respectively
- ‘≤x’ or ‘≥x’: imputation by x.

Toxicity grades and abnormalities for laboratory parameters:

The laboratory abnormalities will be determined according to the criteria specified in the WHO grading table^[6] (see [Attachment 2](#)), available toxicity grades in the laboratory raw data will not be used. In case no toxicity grades are defined for a test, the abnormalities (above/below normal range) will be used.

In determining toxicity grades/abnormalities for each subject the following rules are applied:

- Worst grades/abnormalities are determined over the whole observational period, for treatment phase, follow-up phase and combination of treatment and follow-up phase separately, and including all post-baseline scheduled and unscheduled measurements of that phase.
- The abnormalities “abnormally low” and “abnormally high” are considered equally important, ie, if a subject has as well an abnormally low as an abnormally high value post-

baseline, both abnormalities are shown in the tables. (This implies that the sum of the percentages can be more than 100%)

- If, for a specific test, the grading list provides distinct limits for abnormally low (=hypo) values as well as for abnormally high (=hyper) values, this test should be repeated for hyper and hypo limits separately in cross-tabulations.

Treatment-emergent definition for toxicity grades and abnormalities

An abnormality (toxicity grade or abnormality based on normal ranges) will be considered treatment-emergent if it is worse than the baseline abnormality. If the baseline abnormality is missing, the abnormality is always considered as treatment-emergent. A shift from “abnormally low” at baseline to “abnormally high” post-baseline (or vice versa) is also treatment-emergent.

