In the Phase 2b study 63623872FLZ2002 conducted in acute seasonal influenza A-infected hospitalized adults, among the 64 patients treated with pimodivir 600 mg bid + OST 75 mg bid for 7 days, one had a TEAE corresponding to a grade 3 ALT elevation. The event was considered of mild severity by the investigator, and possibly related to pimodivir and OST. The following confounding factors were noted: OST, paracetamol and clarithromycin use. One patient in the placebo + OST treatment group had a moderate TEAE (grade 2 ALT and grade 3 AST elevation), considered possibly related to placebo by the investigator.

No Hy's law case (>3x ULN ALT + >2x ULN total bilirubin) was reported in the Phase 1 or 2 pimodivir clinical studies.

To date, transaminases elevations remain a potential risk, hence, due to the limited amount of data available, this study will exclude subjects with chronic hepatitis C undergoing hepatitis C treatment and subjects with known severe hepatic impairment (Child Pugh C cirrhosis) (see Section 4.2), and include study treatment hepatic-related discontinuation criteria (see Section 10.2).

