### **10.2. Discontinuation of Study Treatment**

If a subject's study treatment must be discontinued before the end of the treatment regimen, this will not result in automatic withdrawal of the subject from the study.

A subject's study treatment must be discontinued if:

- The investigator believes that for safety reasons or tolerability reasons (eg, AE) it is in the best interest of the subject to discontinue study treatment.
- The subject becomes pregnant.

- The subject experiences any of the following laboratory abnormalities:
  - If baseline AST or ALT within normal range: enzyme activity increases >10x ULN
  - If baseline AST or ALT not within normal range: enzyme activity increases >10x baseline or >500 U/L (whichever occurs first)
  - Total bilirubin increases >5x ULN
  - ALT or AST >3x ULN and total bilirubin >2x ULN

If a subject prematurely discontinues study drug treatment, the subject will be asked to continue with their remaining study visits and assessment schedule. Subjects who withdraw consent during the treatment phase, will be offered an optional Safety Follow-up Visit. The optional Safety Follow-up Visit will occur the day of consent withdrawal or the day after and will consist of the same assessments as at the Final Study Visit (Day 28), with optional PRO completion.

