7.2.2. Analysis Methods

Actual values and changes from baseline will be summarized by treatment group at each scheduled time point, including the safety follow-up visit, the Day 28 final study visit and the last study visit.

A tabulation of the toxicities/abnormalities per timepoint will be presented. This table will also show the number and percentage of subjects per toxicity/abnormality, the number and percentage of subjects per treatment-emergent abnormality, and the cumulative number of subjects per treatment-emergent abnormality per post-baseline timepoint, including the safety follow-up visit, the Day 28 final study visit and the last study visit.

Additionally, a tabulation of the worst toxicity/abnormality will be presented. This table will show the number and percentage of subjects per worst toxicity/abnormality per phase (Treatment phase, Follow-up phase) and for the combination of Treatment and Follow-up phases.

A cross-tabulation of the worst toxicity/abnormality versus baseline will be presented per phase (treatment, follow-up and combination treatment + follow-up). This table will also show the number and percentage of subjects per worst toxicity/abnormality, the number and percentage of subjects per treatment-emergent worst toxicity/abnormality, and the cumulative number of subjects per treatment-emergent toxicity/abnormality.

For tabulations of hyperglycaemia, the results will also be presented for the subgroup of subjects that had been fasting for at least 10 hours.

Mean \pm SE graphs over time for the actual values and changes from baseline will be generated for all tests performed.

A listing of abnormal individual subject hematology and clinical chemistry values from scheduled and unscheduled time points will be provided. This listing will include all other time points for the corresponding subject/parameter.

Grade 3 or higher toxicity laboratory values will be listed separately.

Frequency tables (n %) will be produced for the categorical urinalysis parameters by treatment group at each scheduled timepoint, including the safety follow-up visit, the Day 28 final study visit and the last study visit.

All urinalysis results will be listed.

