ATTACHMENT 2. : WHO TOXICITY GRADING SCALE FOR DETERMINING THE SEVERITY OF ADVERSE EVENTS (FEB 2003)

ABBREVIATIONS (used in the table):

ULN = Upper Limit of Normal

LLN = Lower Limit of Normal

R_x = Therapy

IV = Intravenous

FEV₁ = forced expiratory volume in 1 second

ESTIMATING SEVERITY GRADE

For abnormalities NOT found elsewhere in the Toxicity Tables use the scale below to estimate grade of severity:

GRADE 1	Mild	Transient or mild discomfort (<48 hours); no medical intervention/therapy required.
GRADE 2	Moderate	Mild to moderate limitation in activity; some assistance may be needed; no or minimal medical intervention/therapy required.
GRADE 3	Severe	Marked limitation in activity; some assistance usually required; medical intervention/therapy required; hospitalizations possible.
GRADE 4	Potentially life-threatening^a	Extreme limitation in activity; significant assistance required; significant medical intervention/therapy required; hospitalization or hospice care probable.

^a Revised by the sponsor

COMMENTS REGARDING THE USE OF THESE TABLES

- For parameters not included in the following Toxicity Tables, sites should refer to the “Guide For Estimating Severity Grade” located above.
- Criteria are generally grouped by body system. Some protocols may have additional protocol-specific grading criteria, which will supersede the use of these tables for specified criteria.

Item	Grade 1	Grade 2	Grade 3	Grade 4
Hematology				

Item	Grade 1	Grade 2	Grade 3	Grade 4
Hemoglobin	9.5-10.5 gm/dL	8.0-9.4 gm/dL	6.5-7.9 gm/dL	<6.5 gm/dL
Absolute Neutrophil Count	1,000-1,500/mm ³	750-999/mm ³	500-749/mm ³	<500/mm ³
Platelets	75,000-99,000/mm ³	50,000-74,999/mm ³	20,000-49,999/mm ³	<20,000/mm ³
Prothrombin Time (PT)	≥1.01 to ≤1.25 x ULN	>1.25 to ≤1.50 x ULN	>1.50 to ≤3.00 x ULN	>3.00 x ULN
Activated Partial Thromboplastin Time (aPTT)	≥1.01 to ≤1.66 x ULN	>1.66 to ≤2.33 x ULN	>2.33 to ≤3.00 x ULN	>3.00 x ULN
Fibrinogen	≥0.75 to ≤0.99 x LLN	≥0.50 to <0.75 x LLN	≥0.25 to <0.50 x LLN	<0.25 x LLN
Fibrin Split Product	20-40 mcg/mL	41-50 mcg/mL	51-60 mcg/mL	>60 mcg/mL
Methemoglobin	5.0-9.9%	10.0-14.9%	15.0-19.9%	>20.0%
Liver Enzymes				
AST (SGOT)	≥1.25 to ≤2.50 x ULN	>2.50 to ≤5.00 x ULN	>5.00 to ≤10.00 x ULN	>10.00 x ULN
ALT (SGPT)	≥1.25 to ≤2.50 x ULN	>2.50 to ≤5.00 x ULN	>5.00 to ≤10.00 x ULN	>10.00 x ULN
Gamma-glutamyltransferase	≥1.25 to ≤2.50 x ULN	>2.50 to ≤5.00 x ULN	>5.00 to ≤10.00 x ULN	>10.00 x ULN

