Alkaline Phosphatase	≥1.25 to ≤2.50 x ULN	>2.50 to ≤5.00 x ULN	>5.00 to ≤10.00 x ULN	>10.00 x ULN
Amylase	≥1.1 to ≤1.5 x ULN	>1.5 to ≤2.0 x ULN	>2.0 to ≤5.0 x ULN	>5.0 x ULN
Chemistries				
Hyponatremia	130-135 mEq/L	123-129 mEq/L	116-122 mEq/L	<116 mEq/L or mental status changes or seizures
Hypernatremia	146-150 mEq/L	151-157 mEq/L	158-165 mEq/L	>165 mEq/L or mental status changes or seizures
Hypokalemia	3.0-3.4 mEq/L	2.5-2.9 mEq/L	2.0-2.4 mEq/L or intensive replacement Rx required or hospitalization required	<2.0 mEq/L or paresis or ileus or life-threatening arrhythmia
Hyperkalemia	5.6-6.0 mEq/L	6.1-6.5 mEq/L	6.6-7.0 mEq/L	>7.0 mEq/L or life-threatening arrhythmia
Hypoglycemia	55-64 mg/dL	40-54 mg/dL	30-39 mg/dL	<30 mg/dL or mental status changes or coma
Hyperglycemia (note if fasting)	116-160 mg/dL	161-250 mg/dL	251-500 mg/dL	>500 mg/dL or ketoacidosis or seizures

Item	Grade 1	Grade 2	Grade 3	Grade 4
Hypocalcemia (corrected for albumin)	8.4-7.8 mg/dL	7.7-7.0 mg/dL	6.9-6.1 mg/dL	<6.1 mg/dL or life-threatening arrhythmia or tetany
Hypercalcemia (corrected for albumin)	10.6-11.5 mg/dL	11.6-12.5 mg/dL	12.6-13.5 mg/dL	>13.5 mg/dL or life-threatening arrhythmia
Hypomagnesemia	1.4-1.2 mEq/L	1.1-0.9 mEq/L	0.8-0.6 mEq/L	<0.6 mEq/L or life-threatening arrhythmia
Hypophosphatemia	2.0-2.4 mg/dL	1.5-1.9 mg/dL or replacement Rx required	1.0-1.4 mg/dL intensive Rx or hospitalization required	<1.0 mg/dL or life-threatening arrhythmia
Hyperbilirubinemia	≥1.1 to ≤1.5 x ULN	>1.5 to ≤2.5 x ULN	>2.5 to ≤5.0 x ULN	>5.0 x ULN
BUN	≥1.25 to ≤2.50 x ULN	>2.50 to ≤5.00 x ULN	>5.00 to ≤10.00 x ULN	>10.00 x ULN
CPK*	3 to <6 x ULN	6 to <10 x ULN	10 to <20 x ULN	≥20 x ULN
Creatinine	≥1.1 to ≤1.5 x ULN	>1.5 to ≤3.0 x ULN	>3.0 to ≤6.0 x ULN	>6.0 x ULN or required dialysis
Lipase*	1.1 to <1.5 x ULN	1.5 to <3.0 x ULN	3.0 to <5.0 x ULN	≥5.0 x ULN
* Grading based on Division of AIDS (DAIDS) Table for Grading the Severity of Adult and Pediatric Adverse Events, version 2.0, November 2014.				
Urinalysis				
Proteinuria	1+ or <0.3% or <3g/L or 200 mg – 1 gm loss/day	2-3+ or 0.3-1.0% or 3-10 g/L or 1-2 gm loss/day	4+ or >1.0% or >10 g/L or 2-3.5 gm loss/day	nephrotic syndrome or >3.5 gm loss/day
Hematuria	microscopic only	gross, no clots	gross + clots	obstructive or required transfusion
Cardiac Dysfunction				
Cardiac Rhythm	-	asymptomatic, transient signs, no Rx required	recurrent/persistent; no Rx required	requires Rx

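### SAP 7.2 tabulates ALT, AST and total bilirubin one test at a time, so no summary table states by arm how many subjects met the protocol's joint hepatic criterion

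*SAP*

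**What the plan says.** Protocol 10.2 lists "ALT or AST >3x ULN and total bilirubin >2x ULN" among the laboratory findings that require study treatment to be discontinued. It attaches no timing condition to the two elevations. Protocol 1.4.4 (Increased Transaminases) keeps transaminase elevation as a potential risk. It says there had been no Hy's law case, giving definition and scope as ">3x ULN ALT + >2x ULN total bilirubin) was reported in the Phase 1 or 2 pimodivir clinical studies".

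For the laboratory analysis, SAP 7.2.1 states: "The laboratory abnormalities will be determined according to the criteria specified in the WHO grading" table, with normal-range flags for tests that have no grade. Worst grades take in scheduled and unscheduled post-baseline values. SAP 7.2.2 plans grades per time point, worst grade per phase ("This table will show the number and percentage of subjects per worst toxicity/abnormality per phase"), and worst grade against the same test's own baseline. It adds two listings: "A listing of abnormal individual subject hematology and clinical chemistry values from scheduled and unscheduled time points will be provided", and "Grade 3 or higher toxicity laboratory values will be listed separately".

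In SAP Attachment 2, Grade 2 is ">2.50 to ≤5.00 x ULN" for ALT and for AST, and ">1.5 to ≤2.5 x ULN" for bilirubin.

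Protocol 11.10 leaves the definition of markedly abnormal results to the SAP. SAP 7.2 sets no threshold beyond the WHO grades and the normal ranges.

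**The concern.** The criterion is the sponsor's own, and the ALT form of it is how the protocol summarises liver safety in Phases 1 and 2. The corresponding statement for this trial would be a count in each arm. The planned tables cannot state that count, for two separate reasons. The 3x and 2x ULN cuts fall inside grade bands, so a Grade 2 tally mixes values above and below each cut. The tables also treat tests independently, so they do not show whether raised transaminases and raised bilirubin belong to the same subject.

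Without a planned table, the by-arm number would rest on reading a listing. Whether the two elevations must coincide would be decided after the data are seen, since neither document says. A joint case that is only Grade 2 on each test would look moderate in every table.

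**Working it through.** The documents give no figure to reproduce here. The check is whether the planned tables determine the joint count.

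**Inputs**
- Joint criterion: ALT or AST >3x ULN and total bilirubin >2x ULN (Protocol 10.2).
- ALT and AST bands in x ULN: Grade 1 is 1.25 to 2.5, Grade 2 is >2.5 to 5, Grade 3 is >5 to 10, Grade 4 is >10 (SAP Attachment 2).
- Bilirubin bands in x ULN: Grade 1 is 1.1 to 1.5, Grade 2 is >1.5 to 2.5, Grade 3 is >2.5 to 5, Grade 4 is >5 (SAP Attachment 2).
- Planned arm size: 360 (SAP 1.4), for illustration only.

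**Step 1: place the cuts in the bands.** Since 2.5 < 3 < 5, ALT or AST >3x ULN can be Grade 2, 3 or 4, but Grade 2 also holds values from >2.5 to 3x. Since 1.5 < 2 < 2.5, bilirubin >2x ULN can be Grade 2, 3 or 4, but Grade 2 also holds values from >1.5 to 2x. Neither cut is a grade boundary.

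**Step 2: same tables, different counts.** Take three constructed arms of 360 with AST normal throughout.

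| Arm | Subjects (ALT, bilirubin in x ULN) | ALT table | Bilirubin table | Joint count |
|---|---|---|---|---|
| A | 3 at (4, 1.0); 3 others at (1, 2.2); 354 at (1, 1) | 357 Grade 0, 3 Grade 2 | 357 Grade 0, 3 Grade 2 | 0 |
| B | 3 at (4, 2.2); 357 at (1, 1) | 357 Grade 0, 3 Grade 2 | 357 Grade 0, 3 Grade 2 | 3 |
| C | 3 at (2.7, 1.8); 357 at (1, 1) | 357 Grade 0, 3 Grade 2 | 357 Grade 0, 3 Grade 2 | 0 |

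A and B differ only in whether the elevations share subjects. B and C differ only in where the values sit within Grade 2.

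**Step 3: bounds from the worst-grade tables.** Let T2 and T3 be the numbers of subjects with Grade 2+ and Grade 3+ on ALT or AST, B2 and B3 the same for bilirubin, and N the arm size. For both thresholds exceeded at any time in the phase:

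lower = max(0, T3 + B3 − N); upper = min(T2, B2).

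- T2 = 10, T3 = 3, B2 = 4, B3 = 1, N = 360: lower = max(0, 3 + 1 − 360) = 0; upper = min(10, 4) = 4. Any count from 0 to 4 fits.
- T2 = 0 or B2 = 0: upper = 0, so the count is zero.

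Because ALT and AST are tabulated separately, even T2 is only bracketed by those tables.

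**Step 4: the Grade 3+ listing.** A subject whose worst ALT or AST is >3 to 5x ULN (neither above 5x) and whose worst bilirubin is >2 to 2.5x ULN meets the joint criterion. That subject has no Grade 3 value on any of the three tests, so this listing does not flag the case.

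**Step 5: other SAP outputs.**
- SAP 9.2 tabulates AST, ALT and total bilirubin by AUC12h quartile, again one test at a time. It uses the PD set, a subset of the PK set, which requires a pimodivir dose (SAP 2.2.4, 2.2.5), so there is no placebo comparison.
- The table of AEs with permanent study-drug stop (SAP 7.1.2) depends on there being drug left to stop. Dosing ends on Day 5 or the morning of Day 6 (Protocol 6). Reading the chemistry row of the Time and Events Schedule against the EQ-5D row and its footnote, the post-baseline draws are on Days 3, 6, 14 and 28. Only Day 3 clearly falls within dosing.
- Descriptive statistics by visit leave out unscheduled values (SAP 2.1.5), so a low scheduled maximum does not exclude a case at an unscheduled draw.

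**The case against.** Several objections stand and set the weight of the point.

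- **No requirement is breached.** Protocol 11.10 asks for WHO-grade tabulations, cross-tabulations and listings. It does not promise a joint liver row, and neither document requires stopping criteria to be tabulated by arm. A reader might infer that the SAP contradicts the protocol; it does not.
- **No case is lost.** In any joint case both tests are abnormal, so both appear in the abnormal-value listing with actual values at every time point. A reader might infer that cases would go unseen or that subjects are less protected. The documents do not support that: the stopping rule, AE reporting, follow-up of elevations and IDMC review all operate regardless of these tables.
- **A zero can be inferred by more than one route.** Besides an arm with no Grade 2+ on one side, the per-time-point tables can rule out a same-date case at scheduled visits, and the subgroup laboratory tables can show the two elevations in different subjects. It would be too strong to say the count is known only when one side is empty.
- **The Phase 2b figures do not size the gap.** Protocol 1.4.4 reports 3 of 147 subjects on 600 mg bid with Grade 3+ transaminase TEAEs, and an ALT SAE starting on Day 14. These are transaminase findings, not joint cases. The corresponding single-test results in this trial would already appear in the laboratory and AE tables. No bilirubin rate is given, so no joint count can be projected.
- **The Phase 1 and 2 statement is limited.** It says no case was reported and shows no by-arm table, so it does not establish that this trial would report less than before.

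What survives is narrower: no table in the SAP text states the number, and no timing rule is set in advance.

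**Conclusion.** The point holds as a limited gap in descriptive safety reporting. On the SAP text, no summary table states by arm how many subjects had ALT or AST >3x ULN and total bilirubin >2x ULN, and a case at Grade 2 on every test also misses the Grade 3+ listing. The size is structural: identical planned tables can go with different joint counts (0, 3 and 0 in the example). The counts used above are constructed and predict nothing about this trial, where few true cases are expected.

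The addition is worth making because it is cheap and the criterion is the protocol's own. It touches no efficacy conclusion or error rate. The verdict rests on the SAP text alone: the mock shells (DPS) that SAP 1 mentions are separate, were not available, and may already contain such a table.

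**What to change.** In SAP 7.2.2, keep the WHO-grade tables and add one table by treatment group for the treatment, follow-up and combined phases, using all scheduled and unscheduled post-baseline values. It should give n (%) of subjects with:

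1. ALT or AST >3x ULN;
2. total bilirubin >2x ULN;
3. both, at any time in the phase (the Protocol 10.2 criterion as written, which sets no timing condition);
4. both on the same sampling date, as a stricter row.

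The same-date row should not replace row 3, because with few draws it could leave out subjects who meet the protocol wording. Flag subjects already above a cut at baseline, since chronic liver disease can qualify a subject for entry (Protocol 4.1, criterion 12). List every subject meeting the joint criterion with ALT, AST, total bilirubin and ALP at all time points. Rows for >5x and >10x ULN are unnecessary: they repeat the lower limits of WHO Grades 3 and 4.

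The cost is SAP wording plus the programming of one table and one listing. All four tests are in the central serum chemistry panel (Protocol 9.6.2), so no new samples, visits or staff are needed. If the DPS shells already hold this table, a cross-reference in SAP 7.2.2 with the timing rule stated is enough.

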7.2.2. Analysis Methods

Actual values and changes from baseline will be summarized by treatment group at each scheduled time point, including the safety follow-up visit, the Day 28 final study visit and the last study visit.

A tabulation of the toxicities/abnormalities per timepoint will be presented. This table will also show the number and percentage of subjects per toxicity/abnormality, the number and percentage of subjects per treatment-emergent abnormality, and the cumulative number of subjects per treatment-emergent abnormality per post-baseline timepoint, including the safety follow-up visit, the Day 28 final study visit and the last study visit.

Additionally, a tabulation of the worst toxicity/abnormality will be presented. This table will show the number and percentage of subjects per worst toxicity/abnormality per phase (Treatment phase, Follow-up phase) and for the combination of Treatment and Follow-up phases.

A cross-tabulation of the worst toxicity/abnormality versus baseline will be presented per phase (treatment, follow-up and combination treatment + follow-up). This table will also show the number and percentage of subjects per worst toxicity/abnormality, the number and percentage of subjects per treatment-emergent worst toxicity/abnormality, and the cumulative number of subjects per treatment-emergent toxicity/abnormality.

For tabulations of hyperglycaemia, the results will also be presented for the subgroup of subjects that had been fasting for at least 10 hours.

Mean \pm SE graphs over time for the actual values and changes from baseline will be generated for all tests performed.

A listing of abnormal individual subject hematology and clinical chemistry values from scheduled and unscheduled time points will be provided. This listing will include all other time points for the corresponding subject/parameter.

Grade 3 or higher toxicity laboratory values will be listed separately.

Frequency tables (n %) will be produced for the categorical urinalysis parameters by treatment group at each scheduled timepoint, including the safety follow-up visit, the Day 28 final study visit and the last study visit.

All urinalysis results will be listed.

7.3. Vital Signs

Systolic and Diastolic blood pressure, temperature, pulse rate, respiratory rate will be included in the analysis.

7.3.1. Definitions

Vital Signs abnormalities will be determined according to the WHO grading scale^[6] and the boundaries defined in [Attachment 3](#).

Worst abnormalities are determined over the whole observational period and for each trial phase separately (treatment phase, follow-up phase and combination of treatment and follow-up phases), including all post-baseline scheduled and unscheduled measurements of that phase.

An abnormality (based on normal ranges) will be considered treatment-emergent if it is worse than the baseline abnormality. If the baseline abnormality is missing, the abnormality is always considered as treatment-emergent. A shift from “abnormally low” at baseline to “abnormally high” post-baseline (or vice versa) is also treatment-emergent.

Assessments taken while the subject was not in a supine position will not be included in descriptive statistics but will be considered in determining worst case values.

